### **10.3.8 Additional Efficacy and Pharmacoeconomic Analysis**

The additional efficacy and pharmacoeconomic endpoints of this study are defined in [Section 4.5](#) and details of the analyses are provided in the SAP.

All additional efficacy and pharmacoeconomic analyses will be compared at the 0.05 significance level. These analyses will be used to support the primary and secondary efficacy analysis, therefore, no adjustment for multiplicity will be performed.

### **10.3.9 Safety Analysis**

Safety will be assessed by examination of TEAEs, TEAE of interest, extent of exposure, and changes from Baseline in laboratory values (e.g., selected hematology, chemistry) over time. Furthermore, changes in vital signs of pulse, blood pressure, temperature, and body weight will be monitored.

#### **10.3.9.1 Treatment-Emergent Adverse Events and TEAE of Interest**

Treatment-emergent adverse events will be coded according to MedDRA. TEAEs are defined as events that first occurred or worsened following first dose of study treatment administration. All adverse events recorded as occurring before study treatment administration will be considered Baseline conditions. Related TEAEs are events considered related to study treatment by the investigator (i.e., possibly related, probably related, or related).

The number of events, the number of subjects, and the percentage of subjects who experienced at least one TEAE, incidence rate adjusting exposure will be presented. In addition, TEAEs that are considered by the Investigator to be related to a study drug; TEAEs that lead to early withdrawals; and serious TEAEs will be summarized in the same manner. Frequent TEAEs, including preferred terms with an incidence rate of  $\geq 5\%$  and TEAEs of interest will also be summarized. TEAEs of interest include hypertension, neutropenia, gastrointestinal complaints (nausea, vomiting, diarrhea, and abdominal pain, both overall and separately), infection, and liver function test elevation.

#### **10.3.9.2 Extent of Exposure**

The number of doses of study drug dispensed will be computed for each subject. Summaries will be computed by treatment group based on the Safety Population. Furthermore, the number and percent of subjects experiencing a dose reduction, interruption, or discontinuation of study drug will be presented by treatment group. In addition, a listing of all TEAEs that result in a reduction, interruption, or discontinuation of study drug will be presented. Finally, the reason for drug reduction, interruption, and discontinuation will be tabulated and presented by subject in data listings.

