## **8.0 STUDY DRUG**

### **8.1 Study Drug Description**

Fostamatinib and matching placebo are supplied as orange film coated tablets in 2 dosage strengths: 100 mg and 150 mg. Each bottle of study drug contains 60 tablets. Study drug will be labeled in accordance with Current Good Manufacturing Practices (cGMP)s, local regulatory requirements, and all other applicable laws.

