### **8.3 How Supplied/Study Drug Dispensation**

Fostamatinib and matching placebo are supplied in white opaque HDPE bottles capped with white polypropylene child resistant closures with foil induction seals.

- At Week 0/Baseline, subjects will be randomized via the RTSM system. Two bottles of assigned study drug should be dispensed. The first dose of study drug should be administered in the clinic to ensure that the subject understands dosing instructions
- At the monthly visits (Weeks 4, 8, 12, 16, 20), subjects will be instructed to bring any open bottles containing any unused study drug for accountability. Study drug will be

dispensed to cover dosing until the next visit. Subjects may keep a back up bottle for the duration of the study or until the dose is changed.

- In the event a subject loses a bottle or does not have enough study drug to last until the next monthly visit, one extra bottle of study medication may be dispensed.
- At Week 24, the final bottles dispensed will be collected and reviewed for drug accountability. Any remaining bottles previously dispensed to the subject and not previously collected (such as those dispensed at unscheduled visits or for dose modifications) will be collected for final drug accountability.

Eligible subjects enrolling in the open label extension study will be dispensed a separate supply not used in this study via the RTSM system.

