### **10.3.4 Treatment Compliance**

Subject compliance with the assigned treatment will not be collected in the EDC system. The assessment of compliance will be based on site monitoring and pharmacy drug dispensation logs. All pharmacy logs will be kept in the trial master file.

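### Extent of exposure is measured by doses dispensed, which is supply rather than intake, and the denominator of the exposure-adjusted adverse event rate is not defined

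*Combined protocol and SAP*

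**What the plan says.** Section 10.3.9 makes extent of exposure one component of the safety assessment. Section 10.3.9.2 gives it a single quantitative measure: "The number of doses of study drug dispensed will be computed for each subject". The rest of that section counts subjects with a dose reduction, interruption or discontinuation by arm, and tabulates and lists the reasons. It does not define treatment duration or doses taken, and it does not net out returns.

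The supply rules are in Section 8:

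- Section 8.1: "Each bottle of study drug contains 60 tablets".
- Section 8.3, at Baseline: "Two bottles of assigned study drug should be dispensed".
- Section 8.3, on spare supply: "Subjects may keep a back up bottle for the duration of the study or until the dose is changed". If a bottle is lost or supply runs short, "one extra bottle of study medication may be dispensed".
- Section 8.3, on returns: "At the monthly visits (Weeks 4, 8, 12, 16, 20), subjects will be instructed to bring any open bottles", so that unused drug can be accounted for. Remaining bottles are collected at Week 24.

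On what reaches the database, Section 10.3.4 says: "Subject compliance with the assigned treatment will not be collected in the EDC system". Compliance is followed through site monitoring and pharmacy logs.

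On adverse event rates, Section 10.3.9.1 says only that an "incidence rate adjusting exposure will be presented". It names no denominator and does not refer to Section 10.3.9.2.

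**The concern.** A count of doses dispensed answers how much drug left the pharmacy. An exposure table is read as how much drug subjects took, or how long they were on it. The two differ here by design, because every subject receives two bottles for a first interval that needs less than one, and may hold a spare afterwards.

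The gap is widest where exposure matters most for safety: in subjects who stop early, interrupt, or drop to once-daily dosing. The measure can even move the wrong way. Section 8.3 foresees bottles dispensed for dose modifications, so a reduction that changes tablet strength can add 60 dispensed doses while intake falls. A tablet count also does not separate 100 mg from 150 mg.

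The second gap is the undefined denominator of the adjusted adverse event rate. The only exposure quantity that Section 10 defines is the unsuitable one, so a programmer could reasonably pick it up.

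**Working it through.** The plan states no exposure figure, so there is nothing to reproduce. The check is a direct count.

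**Inputs**

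- 60 tablets per bottle (Section 8.1).
- One tablet per dose; two doses a day on twice-daily dosing (Section 8.4).
- A single dose on Day 1, then twice daily from the next morning (Section 7.2).
- 24 weeks = 168 days (Section 7.3).
- Two bottles at Baseline; later dispensing at Weeks 4, 8, 12, 16 and 20 (Section 8.3, Table 4).
- All subjects start on 100 mg; from Week 4 those tolerating it move to 150 mg twice daily (Section 7.8.1), a separate tablet strength (Section 8.1).
- Bottles per visit after Baseline are not stated, so a range is shown.

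**Doses taken at full twice-daily adherence** = 1 + 2 × (days − 1)

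- First 4 weeks: 1 + 2 × 27 = 55
- 24 weeks: 1 + 2 × 167 = 335
- Stop at Week 2: 1 + 2 × 13 = 27

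**Doses dispensed** = bottles × 60

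- First 4 weeks: 2 × 60 = 120 against 55, a ratio of 2.2.
- Escalated completer: leftover 100 mg tablets cannot supply 150 mg doses at one tablet per dose. Weeks 4 to 24 need 140 × 2 = 280 tablets of 150 mg. Since 280 / 60 = 4.7, that is at least 5 bottles, and with the two from Baseline at least 7.
- Non-escalated completer who uses the second Baseline bottle: 335 / 60 = 5.6, so 6 bottles suffice.

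**Overstatement and conditional effect on a rate.** Overstatement is dispensed / taken − 1. If dispensed doses were the denominator, a rate would be multiplied by taken / dispensed.

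| Completer, fully adherent | Bottles | Dispensed | Taken | Overstatement | Rate factor if dispensed is the denominator |
|---|---|---|---|---|---|
| Stays on 100 mg, uses second Baseline bottle | 6 | 360 | 335 | +7% | 0.93 |
| Escalates at Week 4 | 7 | 420 | 335 | +25% | 0.80 |
| Escalates, 150 mg back-up also issued | 8 | 480 | 335 | +43% | 0.70 |

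If the denominator is time from first to last dose, the factor is 1.00 in every row.

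**Early stoppers**

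- Week 2: 120 / 27 = 4.4
- Week 4, before re-supply: 120 / 55 = 2.2
- Week 12, before re-supply, one bottle at each of Weeks 4 and 8: 240 / 167 = 1.4, with 167 = 1 + 2 × 83

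**Between arms.** Equal inflation cancels in the rate ratio. With an assumed 43% on fostamatinib and 25% on placebo, the ratio is multiplied by 1.25 / 1.43 = 0.87. With the two swapped it is 1.43 / 1.25 = 1.14. Neither split comes from the documents.

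**The case against.** A reader might infer that the exposure-adjusted adverse event rates are understated. The documents do not say so. Section 10.3.9.1 leaves the denominator open and never points to doses dispensed; with ordinary patient-time, back-up bottles have no effect. This objection stands, and the understatement can only be stated as conditional.

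A reader might also infer that the error favours fostamatinib. In the ITP trials in Table 1, events that lead to dose changes were more frequent on active drug (diarrhea 31% against 15%, hypertension 28% against 13%, ALT increase 11% against 0%), so a larger distortion in that arm is plausible. But both arms follow the same bottle rules and the same Week 4 step. The protocol gives no stopping or reduction rates by arm for this trial, and withdrawal for need of other AIHA therapy (Section 7.6) could occur more often on placebo. Neither the direction nor the size is established.

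The 4.4-fold figure at Week 2 describes one hypothetical subject. It is not an arm-level effect, because a pooled rate divides total events by total exposure and such a subject adds little to either.

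Three further points have weight:

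- Section 10.3.9.2 also reports reductions, interruptions and discontinuations by arm, which flags the subjects for whom the count misleads most.
- Event counts and percentages of subjects with events in Section 10.3.9.1 do not depend on exposure.
- Section 10.0 promises a complete SAP before database lock, which may define duration and denominator. Its text is not in the document reviewed.

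None of these changes the fact that Section 10.3.9.2, followed as written, summarises supply. Unlike Sections 10.3.6, 10.3.8 and 10.6, it does not leave the detail to the SAP. Returned tablets are used for compliance monitoring (Sections 8.6 and 10.3.4), but no route into the exposure summary is given.

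**Conclusion.** The point holds for the exposure summary. Dispensed doses overstate intake by at least 25% in a fully adherent completer who escalates at Week 4, by 43% if a 150 mg back-up bottle is also issued, and by about 7% in a non-escalated completer who uses the second Baseline bottle. The excess is larger for early stoppers.

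For the adjusted rates, the finding is that the denominator is undefined. Understatement of about 20% to 30% in escalated completers (1 − 335/420 and 1 − 335/480) would follow only if dispensed doses were used. A bias between arms is possible but not shown.

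These figures assume full adherence and no lost bottles, and take the number of bottles per visit from need or from one bottle per visit. The effect is confined to descriptive safety tables; no efficacy analysis or hypothesis test is touched. The correction should be made before database lock.

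**What to change.** 1. In Section 10.3.9.2 and the SAP, replace doses dispensed with treatment duration: last dose date minus first dose date plus 1. Present it with and without interruption days as defined in Section 7.12, overall and by dose level. Section 7.12 counts only gaps of two or more consecutive days, so isolated missed doses will not be removed; say so in the table footnote.
2. In Section 10.3.9.1, state that this person-time is the denominator of the exposure-adjusted TEAE rate.
3. If a tablet count is kept, report dispensed minus returned, from the accountability already scheduled at Weeks 4 to 24 in Table 4. Use it cumulatively at the end of treatment, because only open bottles are asked for at the monthly visits and a spare may come back much later. Give a rule for lost bottles, which are dispensed but never returned.

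Items 1 and 2 are wording changes. The last dose date should be available, since the follow-up visit is timed from it (Section 7.5). Item 3 costs one added EDC field for returned tablets at visits where the count is already made.

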### **10.3.9.3 Change from Baseline in Laboratory Values**

For selected hematology and chemistry laboratory tests performed, change from Baseline will be calculated for each subject and study visit. Box plots indicating mean and median as well as the 25th and 75th percentiles, and/or spaghetti plots will be presented by treatment group and study visit for both raw values and changes from Baseline.

Summary statistics (i.e., mean, median, standard deviation, maximum, and minimum, 25th and 75th percentiles) for the actual values, changes from Baseline, and maximum value observed post treatment will be tabulated by treatment group and study week. In addition, shifts based on lab values classified per CTCAE criteria V 5.0 at Baseline (i.e., Study Week 0), the maximum grade observed, and the grade observed for the last value post Baseline will be tabulated. New Grade 3 CTCAE on treatment in selected laboratory results will be listed.

### **10.3.9.4 Deaths**

All deaths that occur during the study will be summarized and listed.

### **10.3.9.5 Absolute Neutrophil Count**

Absolute neutrophil count is scheduled to be evaluated at Baseline (i.e., prior to administration of first dose of treatment), and every 2 weeks post randomization (Week 2 to Week 24). Change from Baseline in ANC will be calculated for each subject and study visit. Missing values will be treated as missing.

Summary statistics (i.e., mean, median, standard deviation, maximum, and minimum, 25th and 75th percentiles) for the actual values, changes from Baseline, and maximum value observed post treatment will be tabulated by treatment group and study week. In addition, shifts based on the CTC grades for ANC at Baseline (i.e., Study Week 0), the maximum value observed, and the last value for the post Baseline will be tabulated.

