**Table 1: Incidence of Common ( $\geq 5\%$ ) Adverse Reactions from Double-Blind Clinical Studies (C788-047 and C788-048)**

Adverse Reaction	Fostamatinib (N=102)				Placebo (N=48)			
	Mild %	Moderate %	Severe %	TOTAL %	Mild %	Moderate %	Severe %	TOTAL %
Diarrhea a	21	10	1	31	13	2	0	15
Hypertension b	17	9	2	28	10	0	2	13
Nausea	16	3	0	19	8	0	0	8
Dizziness	8	2	1	11	6	2	0	8
ALT increased	5	6	0	11	0	0	0	0
AST increased	5	4	0	9	0	0	0	0
Respiratory infection c	7	4	0	11	6	0	0	6
Rash d	8	1	0	9	2	0	0	2
Abdominal pain e	5	1	0	6	2	0	0	2
Fatigue	4	2	0	6	0	2	0	2
Chest pain	2	3	1	6	2	0	0	2
Neutropenia f	3	2	1	6	0	0	0	0

ALT = alanine aminotransferase; AST = aspartate aminotransferase

Note: Common adverse reactions were defined as all adverse reactions occurring at a rate of  $\geq 5\%$  of patients in the fostamatinib group and greater than placebo rate.

- Includes diarrhea and frequent bowel movement.
- Includes hypertension, blood pressure (BP) increased, BP diastolic abnormal, and BP diastolic increased.
- Includes upper respiratory tract infection, respiratory tract infection, lower respiratory tract infection, and viral upper respiratory tract infection.
- Includes rash, rash erythematous, and rash macular.
- Includes abdominal pain and abdominal pain upper.
- Includes neutropenia and neutrophil count decreased.

Additional information from the two placebo-controlled Phase 3 ITP studies is provided for the following clinically important adverse reactions: hypertension, hepatotoxicity, diarrhea and neutropenia.

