### 3.6.2.4 Neutropenia

In ITP clinical trials, neutropenia (ANC <1.0 x 10^9/L) was reported. There is no clear association between neutropenia and the risk of infection. Neutropenia occurred in 7% of patients treated with fostamatinib; febrile neutropenia occurred in 1% of patients.

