### 7.5 Study Follow-Up (Week 26 or 2 weeks after Early Termination/Discontinuation)

Subjects who choose not to continue on to the open label study or who have discontinued or terminated the study will return two weeks following the last dose of study drug for follow-up study assessments.

If an SAE is present at the visit, follow-up should occur as indicated in [Section 9.2.1](#).

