### **10.3 Planned Analyses**

All efficacy and safety endpoint parameters will be summarized descriptively. Continuous efficacy and safety endpoints will be summarized using the mean, standard deviation, median, minimum and maximum, 25 and 75 percentiles). Frequency distributions (counts and percentages) will be used to summarize categorical endpoints.

Once all patients complete the study evaluation (i.e., nominal study Week 24 or 26) or prematurely discontinued and the final database is locked, the study will be unblinded and final analyses will be performed. Analysis will be based on nominal study visits (i.e., study Weeks 0 to 26).

The primary efficacy hypothesis tests will be performed using a 2-sided 0.05 significance level. For secondary endpoints, adjustments for the overall type I error will be performed.

It is anticipated that statistical summaries will be performed using SAS Version 9.4 (SAS Institute, Inc., Cary, NC, USA) or higher. Additional software may be used to produce graphics and for statistical methodology not available in SAS.

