Diarrhea	
 
Manage diarrhea using supportive measures (e.g., dietary changes, hydration and/or antidiarrheal medication) early after the onset until symptom(s) have resolved.
 
If symptom(s) become severe (Grade 3 or above), temporarily interrupt study drug.
 
If diarrhea improves to mild (Grade 1), resume study drug at the next lower daily dose (refer to Table 5).
 

Neutropenia	
Neutropenia	
 
If absolute neutrophil count decreases (ANC less than <math>1.0 \times 10^9/L</math>) and remains low after 72 hours, temporarily interrupt study drug until resolved (ANC greater than <math>1.5 \times 10^9/L</math>).
 
Resume study drug at the next lower daily dose (refer to Table 5).
 

ALT = alanine aminotransferase; AST = aspartate aminotransferase; BP = blood pressure; BL = bilirubin; ULN = upper limit of normal; LFT = liver function tests (AST, ALT, total Bi with fractionation if elevated, alkaline phosphatase); AST/ALT = AST or ALT

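### The dedicated ANC table uses each subject's highest neutrophil count, so it does not show the worst neutropenia grade

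*Combined protocol and SAP*

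**What the plan says.** Section 10.3.9.5 is the section dedicated to ANC, which Section 4.4 names as a safety endpoint. ANC is measured at Baseline and every 2 weeks from Week 2 to Week 24. Two outputs use a per-subject extreme:

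- The summary statistics cover actual values, changes from Baseline and the maximum post-treatment value.
- The shift table is described as "shifts based on the CTC grades for ANC at Baseline (i.e., Study Week 0), the maximum value observed, and the last value" after Baseline.

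No per-subject minimum, nadir or worst grade is named.

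Elsewhere the protocol treats low ANC as the problem. Section 3.6.2.4 defines neutropenia as ANC below 1.0 x 10^9/L. Section 7.8.2 lists ANC below 1000/mm³ among the reasons for dose modification. Appendix 2 says that if ANC falls below 1.0 x 10^9/L "and remains low after 72 hours, temporarily interrupt study drug until resolved". Section 10.3.9.1 says "TEAEs of interest include hypertension, neutropenia, gastrointestinal complaints" and other events.

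For other laboratory tests, Section 10.3.9.3 words the shift table differently: "the maximum grade observed, and the grade observed for the last value post Baseline will be tabulated".

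**The concern.** A shift table for a laboratory safety variable should show how far each subject deteriorated from Baseline. For ANC that means the lowest post-Baseline value, or equivalently the highest CTC grade. The highest ANC gives the opposite: a subject with one or several low counts and a normal count at any other visit is graded on the normal count.

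The last-value column does not repair this, because neutropenia that has recovered by the final assessment leaves no trace in it. Recovery is likely, since Appendix 2 interrupts study drug until the count recovers. The last value may also be off drug. Section 10.3 analyses nominal Weeks 0 to 26, and under Section 7.5 subjects who stop early or do not enter the extension "will return two weeks following the last dose of study drug for follow-up study assessments". Section 10.3.9.5 does not say whether that value can be the last one.

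What is at stake is the count of subjects by worst ANC grade and arm, for a known risk of the drug. No efficacy result depends on it.

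**Working it through.** **1. The wording side by side**

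| Section | Harmful direction | Extreme in summary | Shift-table column |
|---|---|---|---|
| 10.3.9.3 Selected laboratory tests | depends on test | maximum value | maximum grade |
| 10.3.9.5 ANC | low | maximum value | grade at maximum value |
| 10.3.9.6 Blood pressure | high | maximum value | category at maximum value |
| 10.3.9.7 Liver function tests | high | maximum value | grade at maximum value |

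The ANC wording matches the two sections where high is bad, which suggests that it was carried over. Section 10.3.9.3 has a form that works in either direction, because a higher grade is always worse.

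**2. What the maximum column can show**

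The largest of a set of values is below 1.0 only if all of them are. Weeks 2 to 24 at 2-week steps give 12 scheduled values. An invented example: 4.0, 3.2, 2.1, 0.8, 1.6, 2.4, 3.0, 3.1, 2.9, 3.3, 3.0, 3.2 (x 10^9/L). The maximum is 4.0 and the last value 3.2, so neither column shows neutropenia. The minimum is 0.8, below the protocol's threshold.

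**3. Size**

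The plan gives no figure to reproduce here. Inputs from the protocol:

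- 45 fostamatinib subjects (Table 2).
- ITP neutropenia rates *p* of 6% (Table 1; the row's footnote reads "Includes neutropenia and neutrophil count decreased") and 7% (Section 3.6.2.4: "Neutropenia occurred in 7% of patients treated with fostamatinib").

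Assumptions that are not in the protocol: the ITP rates apply here, all 12 values are available, and each affected subject has one episode covering *L* = 1 to 3 consecutive visits at a random time.

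Expected subjects with neutropenia: 0.06 x 45 = 2.7; 0.07 x 45 = 3.15.

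A worst-value table shows none with probability (1 − *p*)^45:
- 0.94^45 = 0.06
- 0.93^45 = 0.04

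Under the planned table the maximum column shows none of them, because at least 9 of the 12 values lie outside the episode. The share *s* of affected subjects whose last value is low is:
- *L* = 1: 1/12 = 8.3%.
- *L* = 2: 1/11 = 9.1% if the episode lies wholly within Weeks 2 to 24; 2/12 = 16.7% if it may run past Week 24.
- *L* = 3: 1/10 = 10% to 3/12 = 25%, on the same two readings.

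Expected subjects shown: 2.7 x 0.083 = 0.2 up to 3.15 x 0.25 = 0.8.

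The planned table shows no neutropenia with probability (1 − *p* x *s*)^45:

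| *p* | *s* | *p* x *s* | Probability of none shown |
|---|---|---|---|
| 0.06 | 1/12 | 0.0050 | 0.80 |
| 0.07 | 1/12 | 0.0058 | 0.77 |
| 0.07 | 0.25 | 0.0175 | 0.45 |

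Recovery after interruption, or an off-drug Week 26 value, would lower *s*. Stopping while neutropenic with no later value would raise it.

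**4. Check under a different model**

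A simulation of 200,000 subjects used 12 independent visits and log-normal ANC with median 3.5 x 10^9/L, between-subject log-SD 0.4 and within-subject CV from 20% to 50% (all assumed). The minimum was below 1.0 in 1.3% to 15.7% of subjects, and the maximum in about 0.01% or fewer. Of subjects with a minimum below 1.0, 80% to 86% appeared in neither the maximum nor the last-value column.

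**The case against.** - **The sentence may mean grade.** The shift is between CTC grades, so the maximum could be read as the maximum grade, which is the worst. This is possible, but the text says value, and the preceding sentence uses the same expression where only the ANC value can be meant. A programmer following the text would code the maximum ANC. If grade was intended, the wording still needs correcting.
- **Neutropenia is reported elsewhere.** This is the strongest point, and much of it stands. Neutropenia is an adverse event of interest whose incidence and severity are a safety endpoint (Section 4.4), graded with CTCAE v5.0 as guidance (Section 9.1). Section 7.13.4 requires a result that changes dosing to be recorded as an adverse event, so a persistent ANC below 1.0 that leads to interruption should be captured. Section 10.3.9.2 tabulates interruptions, and the by-visit summaries include the group minimum. Section 10.3.9.3 may cover ANC in its shift table and Grade 3 listing. None of these is certain to supply the missing count. A transient or milder fall that changes nothing need not become an adverse event, a visit minimum is not a count of subjects, and Section 10.3.9.3 covers selected tests without naming ANC.
- **The full SAP may settle it.** Section 10.0 leaves complete detail to a SAP finalised before database lock. Its table specifications could correct the wording, but the protocol text should then agree with them.
- **The size rests on assumptions.** That is so. Episode number, length and timing are assumed, and the rates come from ITP studies with a median exposure of 86 days, against 24 x 7 = 168 planned days here. The percentages describe what one table displays, not the chance that the trial misses neutropenia. Step 2 of the working does not depend on them.
- **Week 26 is an inference.** Section 10.3.9.5 speaks only of Weeks 2 to 24. The off-drug last value is a point to clarify, not a support for the main finding.

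**Conclusion.** The concern holds. As written, Section 10.3.9.5 summarises and grades each subject's best ANC when the harm is a low ANC. That follows from the text alone. Under the stated assumptions, the dedicated table would show on average 0.2 to 0.8 of the 2.7 to 3.2 affected fostamatinib subjects. It would show no neutropenia in 45% to 80% of trials, where a worst-value table would do so in 4% to 6%.

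The consequence is moderate. Other outputs should still bring out most clinically acted-on neutropenia, and no hypothesis test uses this table. The wording should nevertheless be corrected before database lock, because this is the section meant to describe ANC and its likely origin is a simple carry-over.

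**What to change.** In Section 10.3.9.5, replace the maximum value with the minimum post-Baseline value (worst CTC grade) in both the summary statistics and the shift table. Keep the last-value column, and state whether an off-drug Week 26 value can be the last value.

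In Section 10.3.9.3, leave the shift table as it is, since it already uses the maximum grade. In its summary statistics, report the minimum rather than the maximum post-treatment value for tests where low is the risk.

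Carry the same wording into the SAP and table specifications. The cost is a text change and one programming change before database lock. No new data are needed, and no dosing or monitoring rule changes.
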